During FY 2012, 391 patients with implanted port catheters were treated in the OPCC. Seventy of these patients experienced an occlusion of their port that required the administration of alteplase (CathFlo) ([name], personal communication, October 12, 2012). Thus, 70 of 391 experienced an occlusion resulting in an occlusion rate of 18%. Some of these 70 patients experienced an occlusion more than once during that time. Additionally, during that time, a few patients had their implanted port catheters removed due to infection or malfunction. The exact number of patients who experienced multiple occlusions or had their implanted ports removed/replaced during FY2012 is unknown.

During the planning of the current study evaluating implanted port catheters, we engaged the consultation of a biostatistician through the Center for Clinical and Translational Science and Training (CCTST) to conduct a power analysis to

establish the number of participants needed in each group to determine the non-inferiority of the alternative therapy (saline only flush). Consultation was provided by [name], Associate [name] Hospital Medical Center, University of Cincinnati.

Based on the literature and our own experience we estimated an approximate occlusion rate of 20% with the standard treatment (saline + heparinized saline flush as described above). The power analysis conducted by [name] determined that, using a two group normal approximation test of proportions with a one-sided .05 significance level, a sample size of 198 participants per group will have 80% power to reject the null hypothesis that the proposed method is not inferior (i.e. the difference in proportions between the proposed method and the standard method is greater than 0.10). Thus, we will continue to recruit participants in that study until 198 have been enrolled in each group for a total of 396 study participants.

[name] was consulted again when the introduction of the BioFlo Port at TriHealth was discovered. It is [name] recommendation that this second randomized controlled trial using the same methodology and power analysis calculations be conducted. Thus, we will recruit 198 participants per group for a total of 396 participants in this study.

Data Collection:

Independent Variables: Method for flushing implanted port catheters:

- 20 mL of saline followed by 5 mL of Heparinized saline in a concentration of 100 units/mL
OR
- 20 mL of saline only

Dependent Variables:

Primary Outcomes

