- Occurrence of first complete (can neither withdraw blood nor flush the catheter) occlusion
- Occurrence of first partial (able to flush but unable to withdraw blood) occlusion
- Frequency with which alteplase (CathFlo) has to be utilized to resolve an occlusion

Secondary Outcomes

- Number of subsequent occurrences of complete or partial occlusions after the first occurrence.
- Amount of time in days that a port remains patent (flushes easily and able to obtain a blood return).
 - Amount of time between entrance in study and first incidence of partial or complete occlusion

- Amount of time between incidences of partial or complete occlusion.
- Occurrence of other complications:
 - Central Line-Associated Blood Stream Infection (CLABSI) – a laboratory-confirmed (recognized pathogen cultured from one or more blood cultures; organism cultured from blood is not related to an infection at another site) blood stream infection that is considered central line associated (CDC, 2012).
 - Develops complication related to Heparin
 - HIT (Heparin induced thrombocytopenia as measured by a positive HIT antibody test)
 - Other heparin allergy

Moderating variables: other things that could also affect patency of the port

- Number of times port flushed per month or frequency of flushing.
- Use of prophylactic doses of anticoagulant drugs (e.g., enoxaparin, heparin, warfarin)
- Development of a hypercoaguable state, as diagnosed by primary hematologist/oncologist
- Mechanical difficulties related to port placement e.g. “Pinch-off syndrome”
- Length of time port has been in place prior to entrance in study

Extraneous variables:

- Type of cancer
- Age of participant

Data collection tool

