Statistical Analysis: Descriptive statistics will be used to describe the participants. Differences between groups on the dependent variables will be calculated using t-test, Chi-Square or Fisher's exact test as appropriate for the level of data under analysis (also see discussion regarding interim analysis). Regression analysis will be used to determine the effect of the moderating variables on the occurrence of occlusion in the implanted ports. Participants in the

control group and intervention group will be further stratified based on frequency of port flushing. Differences in the rate of occlusion between stratified groups will also be calculated.

Ethical Considerations: The purpose of this study is to determine the safest and most effective flushing solution(s) for maintaining patency in implanted port catheters. In so doing, study participants could be placed at potential risk for catheter occlusion. All catheter occlusion will be treated according to TriHealth policy, i.e., the instillation of alteplase (CathFlo) (see Appendix A). Potential study participants will be made aware of the risk when enrolled in the study (See Appendix B) script for recruiting patients into the study and the Informed Consent Statement).

Informed Consent: Patients who meet inclusion criteria will be approached by a member of the research team who will explain the study, implications of their participation and review the Informed Consent Statement and HIPAA Authorization Forms (see the attached). One signed copy of the Informed Consent Form and HIPAA forms will be given to the study participant and another placed in their folder in the TriHealth Infusion Center to be scanned into their EPIC electronic health record (EHR). The original signed Informed Consent Statement and HIPAA will be stored in a locked drawer in a TriHealth office until the study is completed and closed with the IRB. The RN seeking consent and PI will document the informed consent process in the participant's EHR. Additionally, the blue or yellow sticker on the patient folder in the treatment center and presence of data collection forms in the patient folder will indicate that the patient is a participant in the study.

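### Time between occlusions, and the repeat count if limited to occluders, compare subsets selected by the outcome; only a count over all randomized participants keeps the randomized comparison

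*Combined protocol and SAP*

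**What the plan says.** Under Dependent Variables, the primary outcomes include the first complete occlusion, the first partial occlusion and the frequency of alteplase use. The secondary outcomes include "Number of subsequent occurrences of complete or partial occlusions after the first occurrence" and "Amount of time between incidences of partial or complete occlusion", as well as the time from study entry to the first occlusion.

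The Statistical Analysis section gives one rule for all of these: "Differences between groups on the dependent variables will be calculated using t-test", with chi-square or exact tests where the data call for them. Regression is planned only for the moderating variables. The plan does not say whether a participant without an occlusion counts as zero repeats or is left out. It names no method for recurrent events and gives no rule for a gap cut off by the end of follow-up.

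Two other places bear on the same outcomes. The Data collection tool section stops data collection after alteplase at three consecutive visits, and Experimental Aspect of the Study does so after three consecutive occluded visits. Experimental Aspect of the Study also keeps participants for 12 months or until a listed risk occurs, and the list of risks includes any partial or complete occlusion.

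**The concern.** Randomization protects a comparison of everyone randomized. It does not protect a comparison of those who went on to have an occlusion, because occlusion is the event that the flush may alter.

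For gap time the restriction is built into the definition: at least two occlusions are needed. Complete 12-month data on every participant would not remove it. For the repeat count the restriction depends on a denominator that the plan leaves open, and which could therefore be chosen after the data are seen.

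If saline adds occlusions mainly in ports that would otherwise have stayed clear, those ports enter the saline subset with few repeats and long gaps. They dilute the troublesome ports, and saline can look better among occluders while it causes more occlusions overall. The study aims to change flushing practice and asks about complication rates as well as patency, so a misleading repeat-occlusion result could carry weight.

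**Working it through.** **The plan's own figure.** The Recruitment section plans "using a two group normal approximation test of proportions with a one-sided .05 significance level" and says that "a sample size of 198 participants per group will have 80% power". The inputs are 20% in both arms and a margin of 0.10. Then n = (1.645 + 0.842)² × 2 × 0.20 × 0.80 / 0.10² ≈ 198 per arm, with power 80.0%. The figure reproduces and this point does not change it.

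**Illustration (assumed rates).** The protocol says that the number of patients with multiple occlusions in its historical year is unknown, so the rates below are assumptions. Occlusion counts are Poisson over a full 12 months. A share of 15% of ports is high-risk, at 3 per year in both arms. The other 85% have 0.10 per year with heparin and 0.22 with saline.

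With class weights w and rates λ:
- first-occlusion risk p = Σ w(1 − e^−λ)
- mean total μ = Σ wλ
- repeats per occluder = μ/p − 1
- repeats per randomized participant = μ − p
- risk of at least two occlusions = Σ w[1 − e^−λ(1 + λ)]

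| | Heparin | Saline |
|---|---|---|
| p | 0.1425 + 0.0809 = 0.223 | 0.1425 + 0.1679 = 0.310 |
| μ | 0.45 + 0.085 = 0.535 | 0.45 + 0.187 = 0.637 |
| Repeats per occluder | 0.535/0.2234 − 1 = 1.39 | 0.637/0.3104 − 1 = 1.05 |
| Repeats per randomized participant | 0.312 | 0.327 |
| At least two occlusions | 0.124, or 25 of 198 | 0.138, or 27 of 198 |

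Saline is worse on first occlusion, on total occlusions and on repeats over everyone randomized. Among occluders it looks 25% better (1.05/1.39 = 0.75). A simulation of 2,000,000 participants per arm agrees (1.40 and 1.05).

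**A second model.** This one works visit by visit, with 17 visits 21 days apart, 10% high-risk ports, first-occlusion risk 20% with heparin and 30% with saline, and the saline effect in low-risk ports only (all assumed).
- Repeats per occluder are 0.82 and 0.61, and mean gaps are 98 and 104 days, so saline looks better on both.
- Total occlusions per participant are 0.37 and 0.48, so saline is worse.
- About 16 and 20 participants per arm have a gap.
- In simulated trials of 198 per arm, without the three-visit rule, saline had the lower mean repeats per occluder in about 80% of runs. With all randomized as denominator it was lower in 36%.

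**When the reversal does not occur.** In the first model, raise the high-risk rate under saline from 3.0 to 3.8 per year. Then p = 0.3145, μ = 0.757 and repeats per occluder are 1.41 against 1.39, so the reversal is gone. With a common 2.2-fold increase they are 2.71 against 1.39. In the visit model, a common factor of about 2.0 gives 1.26 against 0.81, and gaps of 75 against 97 days. Saline then had the lower mean repeats per occluder in about 4% of runs. Poisson models with gamma frailty and a common effect (k = 0.3, 1, 5) also kept the correct direction.

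**The three-visit rule.** In the visit model, raising the per-visit risk of high-risk ports from 0.5 to 0.9 lowers observed repeats per randomized participant from 0.44 to 0.24. Without the rule they rise from 0.75 to 1.40. These are raw counts. An offset allows for the shorter follow-up, but the length of that follow-up is itself set by the outcome.

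**The case against.** The strongest reply is that the plan never limits the repeat count to occluders. Someone without an occlusion has zero subsequent occlusions, so the count can be taken over all 198 per arm, and the first illustration then points the right way (0.312 and 0.327). This stands. A reader might infer that the plan compares repeats only among occluders; that is one reading of an open denominator, not stated text. Gap time has no such escape.

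A second reply is that the reversal comes from a chosen pattern in which saline does nothing to high-risk ports. This stands in part. The documents give no repeat-occlusion rates by port risk, and a rise of about a quarter in the high-risk rate (3.0 to 3.8) removes the reversal. The pattern is not far-fetched, though. The protocol lists mechanical problems and hypercoagulable states as influences on patency, and a mechanically troubled port might reocclude whatever the flush.

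A third reply is that frequency of alteplase use, a primary outcome, already approximates total occlusions for everyone. It is a useful companion but not a substitute. The Data collection tool section also gives alteplase for sluggish withdrawal, which falls short of the protocol's definition of partial occlusion, and no analysis with follow-up time is specified for it.

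**Conclusion.** The point holds for time between occlusions under any reading: the planned test is not a randomized comparison, and it would rest on roughly 16 to 27 participants per arm under the assumptions used. It holds for the repeat count only if that count is restricted to occluders; otherwise the defect is an unstated denominator.

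The direction can reverse when the saline effect falls mainly on low-risk ports, and is correct under a uniform effect. Reversal is therefore a possibility that the plan does not guard against, not an expected result. The sizes rest on assumed risk classes, rates and visit spacing.

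A reader might also infer that the non-inferiority conclusion is at risk. The documents do not support this. That conclusion is framed on the occlusion rate, the first-occlusion outcomes can be defined for every randomized participant, and the 198 per arm stands. The point concerns secondary outcomes and should be corrected before analysis.

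**What to change.** - Make the between-arm recurrent outcome the total number of occlusions per randomized participant, scored zero if there were none.
- Estimate the saline-to-heparin rate ratio with a 90% confidence interval, which matches the one-sided 0.05 level. Use a negative binomial model with log follow-up time as offset, or a recurrent-event model with robust variance.
- Report repeats and gap times among occluders by arm as description, with no between-arm test.
- Treat the end of data collection after three consecutive occluded visits as outcome-related, for example as an event in its own right or in a sensitivity analysis. The offset alone is not enough.
- Reconcile the two statements in Experimental Aspect of the Study that, read literally, end participation at any occlusion with the repeat-occlusion outcomes under Dependent Variables. On the literal reading neither repeats nor gaps could be observed.

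The cost is a little more analysis work and the loss of a formal test on gap times. Visit-level patency is already entered on the Record of Flushes while a participant remains under observation, and the sample size does not change.

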Participants in the control group will have yellow colored data collection Face Sheets while participants in the intervention group will have blue colored data collection Face Sheets. The Record of Flushes sheet will be white for patients in both groups. A blue or yellow sticker will be placed on the cover of the patient folder housed in treatment center noting the patient's involvement in the study. The data collection Face Sheet and the current Record of Flushes sheet will be kept in the individual patient folder as long as they remain a participant in the study. As the Record of Flushes data sheet becomes full, they will be collected by study staff and placed in locked drawer in a TriHealth office.

Experimental Aspect of the Study:

Patients who agree to participate in this study will be randomized to either the control group or intervention group as explained above.

Participants in the control group will have their implanted port catheters flushed according to the established TriHealth Nursing Policy: Venous Access Devices (VAD): Care and Maintenance (see Appendix A). Following the use of the port catheter with no continuous fluids running, or before de-accessing a port catheter (removing the port needle), the port will be flushed with 20 ml of normal saline and 5 ml of heparinized saline in the concentration of 100 units of heparin per mL.

Participants in the intervention group will have their ports flushed with normal saline only. That is, following the use of the port catheter with no continuous fluids running, or before de-accessing a port catheter (removing the port needle), the port will be flushed with 20 ml of normal saline. Turbulent flushing technique (the solution is injected using a push/pause technique every 1 mL) will be used in both groups and all accessed port catheters will have a neutral displacement connector. The MicroCLAVE® Clear displacement connector (ICU Medical, Inc., San Clemente, CA, USA) is the current product in use. Participants in both groups will be seen in a TriHealth Cancer Institute Infusion Center at a frequency consistent with their individual treatment plan and as outlined in the TriHealth

Nursing Policy: Venous Access Devices (VAD): Care and Maintenance (see Appendix A). Participants will remain in the study for 12 months or until they experience one of the potential risks noted below. Participants will be considered as having completed the study if they participate for 12 months.

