Potential risks for study participants in either arm of the study include partial occlusion (can instill flush solution but not withdraw blood) and complete occlusion (can neither instill flush solution nor withdraw blood). Study participants could require removal of the port if an occlusion cannot be resolved, and possibly require re-insertion of a new implanted port. In the event of any occlusion, alteplase (CathFlo) in the policy established dose and frequency (see Appendix A) will be instilled to resolve the occlusion. Study participants whose implanted ports are found occluded on three (3) consecutive visits to the treatment center will be excluded from further data collection, i.e., their participation in the study will be terminated. The standard flushing as prescribed by the TriHealth Nursing Policy (see Appendix A) or as prescribed by the attending physician will be used. Study participants whose occlusion cannot be resolved with alteplase and require removal of the port will also be terminated and excluded from further data collection. Patients who develop port infections necessitating port removal will be terminated and excluded from further data collection. Study participants who develop HIT (heparin induced thrombocytopenia) or other heparin allergy will be terminated and excluded from further data collection. Likewise, patients who have thrombotic or embolic phenomenon requiring therapeutic anticoagulation will be terminated and excluded from further data collection.

The study will be closed if there is evidence that study participants in the intervention arm experience implanted port occlusion at a disproportionate rate. The amount of alteplase (CathFlo) used in each group will be assessed each month for monitoring purposes.

The undertaking of this research does require the participation of other personnel, facilities or departments other than those used in data collection. In the event the study participant is admitted to the hospital or requires some intervention using their implanted port catheter (e.g., CT scan with contrast), the study participant will have an information card describing his/her participation in the study and the group to which he/she has been randomized, so that the assigned flush solution is used, and integrity of the study can be maintained. The study participant will receive the card with instructions at the time of his/her enrollment in the study (see Appendix E Wallet Study Card).

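### The outcomes measured in days have no analysis method that handles censoring, and the plan does not say how participants who exit without an occlusion are counted

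*Combined protocol and SAP*

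**What the plan says.** All references are to the combined protocol and SAP.

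- **Secondary Outcomes** (under Dependent Variables) lists the number of days a port stays patent, with two components: "Amount of time between entrance in study and first incidence of partial or complete occlusion" and "Amount of time between incidences of partial or complete occlusion". It also lists "Number of subsequent occurrences of complete or partial occlusions after the first occurrence".
- **Statistical Analysis** states: "Differences between groups on the dependent variables will be calculated using t-test, Chi-Square" or Fisher's exact test, chosen by type of data. No test is paired with a particular outcome. The section adds: "Regression analysis will be used to determine the effect of the moderating variables on the occurrence of occlusion in the implanted ports". The type of regression is not named, and its target is whether an occlusion occurs, not when.
- **Experimental Aspect of the Study** sets follow-up: "Participants will remain in the study for 12 months or until they experience one of the potential risks noted below". It then says: "Potential risks for study participants in either arm of the study include partial occlusion", and adds complete occlusion. Yet it also says: "Study participants whose implanted ports are found occluded on three (3) consecutive visits to the treatment center will be excluded from further data collection". **Data collection tool** has a matching three-visit rule based on alteplase use.
- The same section stops data collection for port infection requiring removal, for HIT or another heparin allergy, and for thrombotic or embolic events needing therapeutic anticoagulation. Each can come before any occlusion.
- The power paragraphs under **Recruitment** give a 20% control rate, a margin of 0.10, one-sided 0.05, 80% power and 198 per group.

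No survival method, analysis population, missing-data rule or dropout allowance appears in the text supplied.

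**The concern.** A time to occlusion is censored for everyone who reaches 12 months, or exits, without one. A t-test needs a number for each person. It must therefore either leave out participants without an occlusion or use their observed patency days whatever ended them. The first choice compares only the minority who occluded and ignores how many did. The second mixes patency with length of follow-up, so a difference between arms in exit can look like a difference in patency.

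The primary proportions have a related but smaller gap. A participant who exits without an occlusion could be counted as occlusion-free or left out of the denominator. The two rules move the result against the 10-point margin in opposite directions, and the plan does not choose between them.

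Finally, if participation ends at the first occlusion, there will be no data on later occlusions or on the time between them.

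**Working it through.** **1. The plan's own figure.** With 20% in both arms, margin 0.10, one-sided 0.05 and 80% power:

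n = 2 × 0.20 × 0.80 × (1.645 + 0.842)² / 0.10² = 197.8, so 198 per group.

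This reproduces the stated number and contains no allowance for exits.

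**2. Extent of censoring.** At 20% risk, 0.80 × 198 = 158 participants per arm have no occlusion time at 12 months, even with no early exit.

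**3. Assumptions for the illustrations.** Constant hazards, h = −ln(1 − p) per year; 198 per arm; a share d of an arm exits evenly over the year. Where the arms differ, the risks are 20% v 30%. The 30% is the margin boundary, not the planning rate. The documents give no exit rate, so every d is an assumption. Time-outcome tests are two-sided 5%, and their rejection rates are simulated.

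**4. Time outcomes, 20% v 30%.** h = 0.2231 and 0.3567.

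- Expected days to occlusion among occluders = 365 × (1/h − (1 − p)/p) = 175.7 v 171.7. A four-day gap is nearly invisible: the t-test rejects about 5-6%.
- Expected patency days capped at 12 months = 365 × p/h = 327.1 v 307.0. With complete follow-up the t-test has power of about 53-54%, log-rank about 63-64%.
- With 20% exit in both arms, the t-test on all patency days falls to about 32%; log-rank stays near 59-60%.

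**5. Time outcomes, no true difference (20% v 20%), t-test on all patency days.**

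| Exit, heparin v saline | t-test | log-rank |
|---|---|---|
| 20% v 20% | 5% | 5% |
| 5% v 0% | about 13% | 5% |
| 10% v 20% | about 32% | 5% |

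**6. Primary proportions, true difference at the margin, nominal one-sided 5%.**

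Observed occlusion share a = (1 − d)p + d(1 − p/h); share exiting without occlusion e = d × p/h.

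- Rule 1 (exits counted occlusion-free): proportion a, n = 198.
- Rule 2 (exits left out): proportion a/(1 − e), n = 198(1 − e).
- False non-inferiority = Φ((0.10 − observed difference)/SE − 1.645), unpooled SE.

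The only exit-related rate in the documents is a HIT incidence of 1-5% among heparin-exposed patients (Background Information/Literature Review). Apply its upper end to the heparin arm alone, d = 0.05:

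- Rule 1: a = 0.95 × 0.20 + 0.05 × (1 − 0.8963) = 0.1952; difference 0.3000 − 0.1952 = 0.1048; SE 0.0431; error 3.9%.
- Rule 2: e = 0.0448; 0.1952/0.9552 = 0.2043; n = 189.1; difference 0.0957; SE 0.0438; error 6.1%.

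At 1% the errors are 4.8% and 5.2%. Larger assumed exits:

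| Exit, heparin v saline | Rule 1 | Rule 2 |
|---|---|---|
| 5% v 5% | 5.6% | 4.7% |
| 10% v 10% | 6.2% | 4.4% |
| 20% v 20% | 7.6% | 3.8% |
| 10% v 20% | 11.4% | 2.2% |
| 20% v 10% | 3.9% | 7.0% |

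**7. Follow-up after an occlusion.** Experimental Aspect of the Study ends participation at any listed risk, and occlusion is one of those listed. The three-visit rules, and the outcomes that count later occlusions, presuppose that follow-up continues after a first occlusion. Both cannot hold.

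**The case against.** **The t-test pairing is inferred.** The plan leaves the choice of test to the type of data and does not name the type of regression. This is fair, but no other listed test suits a time in days, and the regression concerns occurrence. The gap remains.

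**A reader might infer that any t-test on these outcomes is invalid.** The documents do not support that. Days patent, capped at 12 months, is defined for every completer, and the t-test on it keeps its 5% error with complete follow-up or balanced exit. What it loses is power. False rejection needs unequal exit, and the documents give no evidence of the size of any imbalance. Eligibility requires patients to anticipate 12 months of care at the centers, which limits transfers though not deaths. The power contrasts are also superiority comparisons at the margin boundary, for secondary outcomes with no stated power target.

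**A reader might infer that the primary analysis is unsound and should become Kaplan-Meier.** That is not supported either. Counting exits as occlusion-free can be a legitimate estimand, and raw proportions are adequate when losses are small and balanced. Kaplan-Meier assumes that exit is unrelated to occlusion risk, which exits for thrombosis or infection may break. Under an assumed shared gamma frailty (variance 1) and equal exit of 10/20/30%, its error was 5.7/6.4/7.0%, against 5.1/5.2/4.8% for simple exclusion. Exclusion had less power (78/74/69% v 80/78/78%). The choice is a trade-off between estimands, so Kaplan-Meier belongs here only as a sensitivity analysis.

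**Conclusion.** The point holds in two parts of unequal weight, and there is a contradiction to resolve.

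For the outcomes in days, the plan names no method that handles censoring. This does not depend on any exit rate, because about 80% of participants are censored at 12 months at the planning rate. The cost ranges from a moderate loss of power (about 53% v 63%, capped days, complete follow-up) to almost no power (occluders only). The false-rejection figures of 13% and 32% are conditional on assumed unequal exit.

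For the primary proportions, the defect is one unstated counting rule. At the HIT incidence in the documents, applied to the heparin arm alone, the error stays at 3.9-6.1% against 5%, which is small. It matters only with larger or unequal exit.

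The statements on follow-up after an occlusion conflict and must be reconciled. A reader might infer that no data on later occlusions will exist; the documents do not settle this in either direction.

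This should be fixed, with medium confidence. All illustrations rest on constant hazards and assumed exit patterns.

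**What to change.** 1. Analyse time to first occlusion in all randomized participants by Kaplan-Meier with a log-rank test or Cox model, censoring at exit or 12 months.
2. Record the date and reason of every exit, including death and loss to follow-up, and report them by arm.
3. For the primary proportions, state in advance how a participant who exits without an occlusion is counted. Add the Kaplan-Meier 12-month risk difference, with its one-sided 95% upper limit set against 0.10, as a sensitivity analysis and not as a replacement.
4. Reconcile Experimental Aspect of the Study with Secondary Outcomes and Data collection tool on whether follow-up continues after an occlusion. Specify a recurrent-event method for time between occlusions only if it does.

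The cost is some analysis wording and a little data recording. Visit dates are already collected. The appendix forms are not in the supplied text, so it is unknown whether they capture exit dates. Kaplan-Meier and log-rank rest on exit being unrelated to occlusion risk; the plan should say so and use the exit reasons to judge it.
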